**Unlikely (must have 2)**

- Does not have a temporal relationship to the intervention
- Could readily have been produced by the subject's clinical state
- Could have been due to environmental or other interventions
- Does not follow a known pattern of response to intervention
- Does not reappear or worsen with reintroduction of intervention

**Unrelated**

- The temporal relationship between treatment exposure and the adverse event is unreasonable or incompatible and/or adverse event is clearly due to extraneous causes (e.g., underlying disease, environment)

**11.1.3 Serious Adverse Event (SAE)**

Adverse events are classified as serious or non-serious. A *serious adverse event* is any AE that is:

- Fatal
- Life-threatening
- Requires or prolongs hospital stay
- Results in persistent or significant disability or incapacity
- A congenital anomaly or birth defect
- An important medical event

Any adverse event that results in hospitalization or prolonged hospitalization should be documented and reported as a serious adverse event unless specifically instructed otherwise in this protocol. Any

condition responsible for surgery should be documented as an adverse event if the condition meets the criteria for an adverse event.

Neither the condition, hospitalization, prolonged hospitalization, nor surgery are reported as an adverse event in the following circumstances:

- Hospitalization or prolonged hospitalization for diagnostic or elective surgical procedures for a preexisting condition. Surgery should *not* be reported as an outcome of an adverse event if the purpose of the surgery was elective or diagnostic and the outcome was uneventful.
- Hospitalization or prolonged hospitalization required to allow efficacy measurement for the study.
- Hospitalization or prolonged hospitalization for therapy of the target disease of the study, unless it is a worsening or increase in frequency of hospital admissions as judged by the clinical investigator.

All adverse events that do not meet any of the criteria for serious event should be regarded as *non-serious adverse events*.

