## 5.7 Study Endpoints

Consistent with the study objectives, the primary endpoints will focus on the safety and tolerability of AVT001 treatment versus placebo.

The primary endpoints are:

- (a) The incidence of treatment-emergent adverse events (TEAEs).
- (b) Changes from baseline in clinical laboratory parameters.
- (c) The incidence and severity of local IV-site reactions.
- (d) Changes from baseline in vital signs and electrocardiograms.
- (e) Incidence of severe hypoglycemic events.

Secondary objectives focus on the CD8+ T-cell regulatory system and therapeutic outcomes associated with T1D. These pharmacodynamic effects of AVT001 will be assessed in an exploratory manner.

Secondary endpoints will include:

- (a) Assessment of the HLA-E-restricted CD8+ T cell regulatory activity (“potency assay”)
- (b) Changes from baseline in the area under the curve (AUC) of the stimulated C-peptide levels over the first 4 hours of a mixed meal tolerance test (MMTT)
- (c) Changes from baseline in HbA1c
- (d) Change from baseline in total daily insulin dose
- (e) Changes from baseline in autoantibody levels

The primary time point for analysis is Month 5, at which point the primary assessment of the study objectives is performed.

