#### 11.1.2 Adverse Event

Adverse event means any untoward medical occurrence associated with the use of a drug in humans, whether or not considered drug related. Adverse events may include safety findings considered to be clinically significant by the Investigator. An adverse drug event can therefore be any unfavorable and unintended sign (including an abnormal laboratory finding), symptom, or disease temporally associated with the use of a medicinal product, whether or not it is related to the medicinal product. Reporting an adverse event does not necessarily reflect a conclusion by the Investigator that the event is causally related to the drug.

AE is any symptom, sign, illness or experience that develops or worsens in severity during the course of the study. Intercurrent illnesses or injuries should be regarded as adverse events. Abnormal results of diagnostic procedures are considered to be adverse events if the abnormality:

- results in study withdrawal
- is associated with a serious adverse event
- is associated with clinical signs or symptoms
- leads to additional treatment or to further diagnostic tests
- is considered by the investigator to be of clinical significance

A preexisting condition is one that is present at the start of the study. A preexisting condition should be recorded as an adverse event if the frequency, intensity, or the character of the condition worsens during the study period.

Each adverse event in this study will be assessed for Grade, where Grade of an AE refers to the severity of the AE. Grade will be assessed according to CTCAE Version 4.03 or higher. The CTCAE displays Grades 1 through 5 with unique clinical descriptions of severity for each AE that are based on this general guideline, with higher grades indicating worse severity.

The relationship of any AE to study treatment will be assessed using the following definitions:

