#### **17.1.5. SEVERE HYPOGLYCAEMIC ADVERSE EVENTS**

Severe hypoglycaemic adverse events will be the AEs coded to the “Hypoglycaemia” Preferred Term (PT). A listing of all severe hypoglycaemic events will be provided. A summary table of severe hypoglycaemic adverse events may be provided if needed.

Author:	[name]	Version Number:	2.0
Template No.:	CS_TP_BS016 Revision 6	Version Date:	23Nov2022
Effective Date:	02Dec2019	Reference:	CS_WI_BS005

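### Section 11.1.3 leaves it to an undefined investigator judgement whether a type 1 diabetes admission is reported as an AE or SAE, and SAP 17.1.5 carries that gap into the severe hypoglycaemia endpoint

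*Combined protocol and SAP*

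**What the plan says.** Section 11.1.3 of Protocol Amendment 3 starts from a general rule: an AE that leads to hospitalisation "should be documented and reported as a serious adverse event unless specifically instructed otherwise in this protocol". It then lists exemptions, introduced by "Neither the condition, hospitalization, prolonged hospitalization, nor surgery are reported as an adverse event in the following circumstances". One of them is "Hospitalization or prolonged hospitalization for therapy of the target disease of the study, unless it is a worsening"; the limit in full is "unless it is a worsening or increase in frequency of hospital admissions as judged by the clinical investigator". Neither worsening nor the reference period for frequency is defined.

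Section 11.1.2 pulls the other way: "A preexisting condition should be recorded as an adverse event if the frequency, intensity, or the character of the condition worsens during the study period". Section 11.2 requires every AE in the study period to be recorded.

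Section 5.7 lists TEAE incidence and "Incidence of severe hypoglycemic events" among the primary endpoints. Sections 8.3.1, 8.4.1, 8.4.2 and 11.1.7 and Table 3 collect severe hypoglycaemia as its own item at study visits from Day 1. Section 9.6 tabulates it by the definition in 11.1.7. SAP v2.0, section 17.1.5, takes another source: "Severe hypoglycaemic adverse events will be the AEs coded to the" Hypoglycaemia Preferred Term. It promises a listing, and a summary table only if one is needed. SAP v1.0 has the same rule.

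**The concern.** The exemption covers the disease under study. All subjects are within 12 months of diagnosis at first dosing, so an admission for diabetes is one of the serious events one would expect to see. The placebo arm is there to separate background diabetes events from treatment effects. A filter applied when the site decides what to report removes events before that comparison can be made. It is not needed for attribution, because the causality scale in 11.1.2 already lets the investigator classify an event as due to underlying disease.

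The AE record also feeds more than the tables. SAEs are read from the AE page of the eCRF (SAP 17.1.3), potential dose-limiting toxicities are flagged on that page (SAP 17.1), and the stopping rule in 5.6.1 counts dose-limiting toxicities. The sponsor and FDA reporting routes in 11.3 start from reported events. The DSMB reports were generated from the EDC system (SAP 4.1). An admission that is not entered as an AE is absent from all of these.

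**Working it through.** This is mainly a question of wording, so the first step is to follow two kinds of event through the rules.

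**Ketoacidosis admission after an infusion**

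1. General rule in 11.1.3: a hospitalised AE is an SAE, unless the protocol instructs otherwise.
2. Exemption: treatment of type 1 diabetes is treatment of the target disease, so the exemption is in play.
3. Limit: if the investigator judges it a worsening, or admissions more frequent, it is reported. 11.1.2 supports reporting, but uses the same undefined idea of worsening.
4. If the investigator regards it as the expected course of recent-onset diabetes, neither the admission nor the condition is reported.
5. Back-up: the documents do not mention ketoacidosis and give it no collection field. AE/SAE reporting is the only route.

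**Admission for severe hypoglycaemia**

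1. Whether this is therapy of the target disease is open to reading.
2. If it is exempted, the event is still captured by the visit question and tabulated under protocol 9.6.
3. SAP 17.1.5 selects from AEs by Preferred Term, so the same event would be absent from the SAP's output for this primary endpoint and from the SAE tables.

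**Size of one missed event.** Planned numbers are 16 on AVT001 and 8 on placebo (protocol 5.3).

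- AVT001: 1/16 = 6.3 percentage points.
- Placebo: 1/8 = 12.5 percentage points.

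**Effect on the plan's own detection figure.** Protocol 9.2 states at least 80% probability of seeing one or more cases of an event with 12% incidence in 14 AVT001 subjects.

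- Reproduced: 1 − (1 − 0.12)^14 = 1 − 0.88^14 = 83.3%. The stated figure is correct.
- The 80% level needs a reported incidence of at least 1 − 0.20^(1/14) = 10.9%.
- Illustration: suppose a share f of subjects with such an event goes unreported (f is assumed; the documents give no value). The probability becomes 1 − (1 − 0.12(1 − f))^14.

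| f (assumed) | reported incidence | probability of at least one in 14 |
|---|---|---|
| 0% | 12.0% | 83.3% |
| 10% | 10.8% | 79.8% |
| 25% | 9.0% | 73.3% |
| 50% | 6.0% | 58% |
| 75% | 3.0% | 34.7% |

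**How many admissions might be at issue.** Assume a 5% to 10% risk per subject of any diabetes admission over 24 months.

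- Over 24 months in 24 subjects: 24 × 0.05 = 1.2 to 24 × 0.10 = 2.4.
- The TEAE window closes 30 days after the last dose, at about Day 90 of 720. At a constant rate, 1.2 × 90/720 = 0.15 to 2.4 × 90/720 = 0.30 fall inside it. The rest would belong in the post-treatment tables.
- These are counts of all diabetes admissions, so they are upper limits for what the clause could exempt.

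**The case against.** The strongest reply is that the exemption has a limit and that other rules narrow it further. A new ketoacidosis admission, in a subject screened against poorly controlled diabetes, would ordinarily be a worsening. 11.1.2 would then make it an AE. 11.1.2 and 11.1.6 also turn abnormal results into AEs when they need treatment or active management. That stands for the ordinary case, and a careful site would probably report. It does not close the gap: 11.1.3 is the specific instruction for admissions, and its limit rests on judgement without criteria.

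A second reply is that faster beta-cell loss would show in MMTT C-peptide, HbA1c and insulin use. That is so, but those measures do not count admissions and do not feed dose-limiting toxicity flagging or expedited reporting.

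A third is that the SAP's use of coded AEs differs from protocol 9.6 even without the exemption. That is correct, and it is a reason to repair SAP 17.1.5 in its own right.

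Three stronger readings are tempting and are not supported:

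- A reader might infer that severe hypoglycaemia goes unrecorded. It has its own item at study visits, with no exception for hospitalised events.
- A reader might infer that 11.1.3 contradicts itself. Its general rule expressly yields to specific instructions, and the exemption is one.
- A reader might infer that the clause can remove every diabetes admission. By its own terms it cannot remove those judged a worsening or an increase in frequency.

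**Conclusion.** The point holds in a limited form. Reporting of diabetes admissions, ketoacidosis above all, depends on an undefined judgement in a trial whose primary endpoints are safety, and ketoacidosis has no other route into the data. For severe hypoglycaemia the weakness is narrower: possible loss from SAE reporting, and an SAP derivation that ignores the collection made for the purpose.

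The size per missed event is 6.3 percentage points on AVT001 or 12.5 on placebo. The total cannot be estimated, because the documents give neither an admission rate nor the share that sites would treat as exempt; the detection probabilities and expected counts above rest on assumed values. Investigators are blinded in the treatment period, so omissions would be expected to thin both arms rather than favour one. The sample-size statement is unaffected.

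**What to change.** 1. In protocol 11.1.3, limit the target-disease exemption to planned or elective admissions. State that every unplanned diabetes-related admission is recorded as an AE and reported as an SAE, with relatedness left to the existing causality scale. Put the same line in the eCRF guidance.
2. In SAP 17.1.5, derive the severe hypoglycaemia endpoint from the visit collection under 11.1.7, so that it agrees with protocol 9.6, and make the summary table definite.
3. The Month 5 analysis has already been delivered, but SAP v2.0, section 4.4, foresees a further SAP amendment before the Month 24 lock. Use it for item 2, and ask the site to check retrospectively for unplanned diabetes admissions that were not entered.

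The cost is a sentence in an amendment, a changed derivation, a record check for about 24 subjects and a few more SAE forms.

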#### **11.1.4 General Physical Examination Findings**

At screening, any clinically significant abnormality should be recorded as a preexisting condition. At the end of the study, any new clinically significant findings/abnormalities that meet the definition of an adverse event must also be recorded and documented as an adverse event.

Physical examinations can be symptom-driven except at Screening, Month 5, and Month 12, during which full examinations are required.

#### **11.1.5 Post-study Adverse Event**

All unresolved adverse events should be followed by the investigator until the events are resolved, the subject is lost to follow-up, or the adverse event is otherwise explained. At the last scheduled visit, the investigator should instruct each subject to report any subsequent event(s) that the subject, or the subject's personal physician, believes might reasonably be related to participation in this study. The investigator should notify the study sponsor of any death or adverse event occurring at any time after a subject has discontinued or terminated study participation that may reasonably be related to this study. The sponsor should also be notified if the investigator should become aware of the development of cancer or of a congenital anomaly in a subsequently conceived offspring of a subject that has participated in this study.

#### **11.1.6 Abnormal Laboratory Values**

A clinical laboratory abnormality should be documented as an adverse event if any one of the following conditions is met:

- The laboratory abnormality is not otherwise refuted by a repeat test to confirm the abnormality
- The abnormality suggests a disease and/or organ toxicity
- The abnormality is of a degree that requires active management; e.g. change of dose, discontinuation of the drug, more frequent follow-up assessments, further diagnostic investigation, etc.

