### 11.1.7 Severe Hypoglycemia

Subject self-monitoring of blood glucose will be performed according to the standard of care as indicated by the investigator. This may include clinician-prescribed glucose monitoring devices, ie, glucose meters or continuous glucose monitoring devices (CGM). The number of severe hypoglycemic events will be collected as part of each study visit. Events are defined according to American Diabetes Association recommended criteria.

- Severe hypoglycemia denotes severe cognitive impairment requiring external assistance for recovery. Severe hypoglycemia is an event requiring assistance of another person to actively administer carbohydrates, glucagon, or take other corrective actions. Plasma glucose concentrations may not be available during an event, but neurological recovery following the return of plasma glucose to normal is considered sufficient evidence that the event was induced by a low plasma glucose concentration.
- In addition to the above criterion, for subjects using CGM, readings below the  $<54$  mg/dL (3.0 mmol/L) for at least 15 minutes will be considered severe hypoglycemia

Note that non-severe hypoglycemic events will not be collected or recorded in the study database, but that the investigator will monitor those types of events according to the site's standard of care.

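### Protocol 11.1.6 makes any unrefuted laboratory abnormality an adverse event, is not reconciled with 11.1.2 or 11.1.7, and may inflate and dilute overall TEAE incidence in both arms

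*Combined protocol and SAP*

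**What the plan says.** Three current sections of Protocol Amendment 3 bear on whether a laboratory result is an adverse event.

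- **11.1.6 Abnormal Laboratory Values:** "A clinical laboratory abnormality should be documented as an adverse event if any one of the following conditions is met". The first condition is "The laboratory abnormality is not otherwise refuted by a repeat test to confirm the abnormality". The other two concern abnormalities that point to disease or organ toxicity and those that need active management. The term abnormality is not defined.
- **11.1.2 Adverse Event:** "Abnormal results of diagnostic procedures are considered to be adverse events if the abnormality" meets one of five conditions: study withdrawal, association with a serious event, association with signs or symptoms, further treatment or tests, or that it "is considered by the investigator to be of clinical significance". The general definition in the same section also covers "any unfavorable and unintended sign (including an abnormal laboratory finding"). On existing problems it says "A preexisting condition should be recorded as an adverse event if the frequency, intensity, or the character of the condition worsens".
- **11.1.7 Severe Hypoglycemia:** "Note that non-severe hypoglycemic events will not be collected or recorded in the study database".

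Protocol 5.7 puts TEAE incidence first among five primary endpoints and the incidence of severe hypoglycaemic events last. Protocol 9.6 tabulates severe hypoglycaemia by the 11.1.7 definition. SAP v2.0, section 17.1.5, instead takes every adverse event coded to the Hypoglycaemia preferred term, with no severity condition.

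**The concern.** The conditions in 11.1.6 are alternatives, so the first is enough alone. The documents contain no rule that requires a confirmatory repeat, so a value that nobody repeats is also unrefuted. A minor, symptomless abnormality that leads to no action is then an adverse event under 11.1.6 while meeting nothing on the 11.1.2 list. The count behind primary endpoint (a) depends on which text the investigator follows.

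At stake is the interpretability of the overall TEAE percentage. Background laboratory events raise it in both arms and shrink any difference between them. Primary endpoint (e) is also exposed. Glucose is in the metabolic panel, so a low laboratory value could be recorded under 11.1.6, coded to Hypoglycaemia, and listed as severe under SAP 17.1.5 although it does not meet 11.1.7.

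Two SAP defaults could add to this. A missing grade is set to grade 3 (17.1.1.1) and a missing relationship is counted as related (17.1.1.2). If laboratory-only events lacked those fields, the severity and relatedness tables would be inflated too.

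**Working it through.** **1. The plan's own figure.** Protocol 9.2 and SAP 7.1 claim at least 80% probability of seeing at least one event of 12% incidence among 14 subjects on AVT001.

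1 − (1 − 0.12)^14 = 1 − 0.88^14 = 0.833.

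This is reproduced. The inflation for 10% dropout also holds: 21/0.9 = 23.3, rounded up to 24, or 16 and 8 at 2:1. Neither figure depends on the laboratory rule.

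**2. The same result under each text.**

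| Result | 11.1.6 | 11.1.2 list | 11.1.7 and SAP 17.1.5 |
|---|---|---|---|
| Minor abnormality, not repeated, no symptoms, no action, not judged significant | Adverse event | No condition met | Not applicable |
| Low laboratory glucose, non-severe | Adverse event if unrefuted | Only if a listed condition is met | Not recorded under 11.1.7; listed as severe under SAP 17.1.5 if recorded and coded to Hypoglycaemia |

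**3. Possible size.** P(at least one laboratory adverse event) = 1 − (1 − q)^(m × v).

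- m = number of effectively independent analytes. SAP v2.0 Appendix 2 lists 16 chemistry + 10 haematology + 3 urine = 29.
- v = laboratory visits that can yield a TEAE. Dosing-day samples precede the infusion (protocol 8.3.1), so Day 1 cannot count. Days 30 and 60 can. Day 90 ± 7 can fall outside the window, which closes 30 days after the last dose (protocol 9.5). So v is 2 or 3; v = 1 is shown as a low case.
- q = chance that one result is a new abnormality. **The documents give no value.** I assume 1%, 2.5% and 5%, the last being the share outside a 95% reference range with no drug effect.

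| m | v | q = 1% | q = 2.5% | q = 5% |
|---|---|---|---|---|
| 29 | 1 | 25.3% | 52.0% | 77.4% |
| 29 | 2 | 44.2% | 77.0% | 94.9% |
| 29 | 3 | 58.3% | 88.9% | 98.8% |
| 27 (without glucose and HbA1c) | 3 | 55.7% | 87.1% | 98.4% |
| 10 (allowing for correlation) | 3 | 26.0% | 53.2% | 78.5% |

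For example, 29 × 3 = 87 results and 1 − 0.95^87 = 0.988. The table runs from about 25% to 99%. This illustrates assumptions and is not a bound.

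**4. Dilution.** Assume true TEAE rates of 70% and 40%, and laboratory events independent of these with the same probability L in both arms. Each observed rate is 1 − (1 − rate)(1 − L), so the difference is 0.30 × (1 − L).

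- L = 40%: 0.30 × 0.60 = 18 points
- L = 77%: 0.30 × 0.23 = 6.9 points
- L = 95%: 0.30 × 0.05 = 1.5 points

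**The case against.** The strongest reply is that this is loose drafting with limited consequences. Much of that stands.

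- Section 11.1.2 does not say that its five conditions are the only route, and its general definition admits abnormal laboratory findings. Part of the inconsistency is therefore inside 11.1.2. This weakens the idea of a clean narrow rule against a broad one, but it adds another reading and settles nothing.
- Equating abnormality with a value outside the reference range is an interpretation. The SAP uses normal ranges and CTCAE grades only for shift tables.
- Pre-existing problems count only on worsening, and the SAP Appendix 1 note treats events that began before dosing the same way. Raised glucose and HbA1c in diagnosed type 1 diabetes would often be present at baseline, so they do not automatically create TEAEs.
- The conflict with 11.1.7 is confined to a low laboratory glucose.
- The rule is the same in both arms, the SAP names one investigator at one centre, and safety is not tested between arms.
- TEAEs are also shown by system organ class and preferred term, maximum severity and relatedness, and laboratory data have their own shift tables.

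A reader might infer three stronger conclusions. The first is that TEAE incidence approaches 100% in both arms. The documents give no abnormality rate, and only the upper end of the assumptions gets there. The second is that the sample-size sentence loses its meaning. It does not: it concerns an event of 12% incidence and still gives 83.3%. The third is that the trial could not separate AVT001 from placebo on safety. The more detailed tables can still show a signal.

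**Conclusion.** The inconsistency is real and in current text. Read literally, 11.1.6 makes every unrefuted laboratory abnormality an adverse event, without reconciliation to the 11.1.2 list or, for a low laboratory glucose, to 11.1.7. SAP 17.1.5 carries the glucose problem into primary endpoint (e) by dropping the 11.1.7 definition that protocol 9.6 relies on.

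The supportable conclusion is that overall TEAE incidence may be substantially inflated and a difference between arms diluted. The figure of about 25% to 99% of subjects with a laboratory event rests on assumed values of q and m and on independence between results. The damage is to a descriptive primary endpoint. It does not bias a test, and it changes no planned sample size. That is more than missing detail, because a stated rule shapes a primary endpoint.

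Timing limits the remedy. SAP v2.0, section 4.2, records the data lock on 29 April 2022 and unblinding on 17 May 2022, after the last subject's Month 5 visit. The TEAE window had then closed for every subject, so recorded TEAEs should not be redefined.

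**What to change.** 1. **Protocol clarification.** Reconcile 11.1.6 with the 11.1.2 list so that one stated rule governs recording from now on, and define laboratory abnormality. State how a low laboratory glucose is handled consistently with 11.1.7. At this stage the change can affect only post-treatment events, so give its effective date in those tables.
2. **SAP 17.1.5.** Restrict severe hypoglycaemia to events that meet the 11.1.7 definition, in line with protocol 9.6.
3. **Day 360 and final analyses.** Keep the TEAE table as recorded. Add one sensitivity table of TEAE incidence excluding laboratory-only events. Staff blinded to treatment should identify these by preferred term, with the list fixed before each lock. Preferred term is the practical route because nothing in the documents shows that the CRF captures which 11.1.6 condition led to recording.

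The cost is a clarification letter, a short SAP edit and one extra table. The excluded abnormalities remain visible in the planned laboratory shift tables.
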